#### 9.6 Interim Analyses

Interim analyses are planned after each 80 subjects (40 per arm) have completed the primary endpoint, until 320 total subjects or the non-inferiority for the primary endpoint is met (whichever occurs first).

Additionally, sample size re-assessments will be carried out during interim analyses. The conditional power will be calculated to determine if a sample size adjustment is necessary. There will not be necessary to adjust the alpha level if the conditional power is greater than 50% (i.e., within the promising zone). If the chance of success is too low (i.e. <10%), *early stopping for futility may be considered*.

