#### **8.7 Subject Selection and Enrollment**

After being informed of the nature of the study, the subject will sign a written informed consent form (ICF) that has been approved by the appropriate IRB of the respective clinical site. Enrollment of up to 320 subjects is planned. Interim analyses will be performed every 80 subjects (40 per arm) to reassess sample size based on a Bayesian adaptive design.

Subjects' participation in the study will last approximately 5–6 weeks, including bowel preparation, CCE or CTC, both blinded and unblinded OC procedures, and follow-up 5-9 days post-OC procedure via telephone.

Subjects who meet all inclusion criteria, but no exclusion criteria, will be eligible for participation in the study.

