## 9.0 Statistical Analysis

### 9.1 Sample Size Determination

The sample size is estimated based on the primary non-inferiority hypothesis under a Bayesian adaptive design. Interim assessments will be performed at every 80 subjects (40 per arm) with a maximum of 320 subjects (160 per arm). Early success will be claimed if the pre-defined success criterion is met.

The following parameter assumptions are used in the estimation, based on prior literature (15).

- Predicted CCE diagnostic yield: 25%
- Predicted CTC diagnostic yield: 15%
- Noninferiority hypothesis with a 5% margin
- Accounting for approximately 10% attrition

With the assumptions, a total of 320 subjects (160 per arm) with interim assessments at every 80 subjects (40 per arm) will provide more than 80% power to test the primary hypothesis at the significance level of 5%.

Note that the expected sample size will be smaller than 320 with the adaptive Bayesian design since an early interim claim for success is possible. Additionally, if non-inferiority is proven, superiority will also be tested (which is not statistically powered at 80%).

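### Section 9.6 plans sample-size re-assessment without reconciling it with the 320-subject maximum, and its general waiver of alpha adjustment does not hold for every multi-look extension the text leaves open

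*Combined protocol and SAP*

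**What the plan says.** Section 9.1 fixes the design: "Interim assessments will be performed at every 80 subjects (40 per arm) with a maximum of 320 subjects (160 per arm"). Section 8.7 agrees on the ceiling ("Enrollment of up to 320 subjects is planned"), and so does the Synopsis. Section 9.6 runs the interims "until 320 total subjects or the non-inferiority for the primary endpoint is met (whichever occurs first").

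Two statements sit beside this ceiling. Section 8.7 gives the purpose of the interims as "to reassess sample size based on a Bayesian adaptive design". Section 9.6 adds: "Additionally, sample size re-assessments will be carried out during interim analyses". It makes conditional power the test of whether the size needs adjusting, and then states: "There will not be necessary to adjust the alpha level if the conditional power is greater than 50% (i.e., within the promising zone"). Futility is handled separately, as an option when the chance of success is below 10%.

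Section 9.2 sets the success rule: a posterior probability of non-inferiority of at least 98% at an interim or 96% at the final analysis. It says these values keep the false positive rate under control. Section 9.1 gives the significance level as 5%, without saying whether it is one- or two-sided, and power above 80%.

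**The concern.** Enrolment already runs to 320 unless success or futility ends it sooner. A rule for favourable interim results therefore has no function unless the trial can grow past 320. The term promising zone, which normally describes a sample-size increase, points the same way.

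If growth is intended, error control depends on details that the plan does not give:

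- the new maximum;
- the effect assumed in conditional power;
- which interims may trigger a change;
- whether the 98% looks continue after an increase;
- what happens when conditional power lies between 10% and 50%.

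Section 8.10.3 says that neither subject nor investigator is blinded to arm. An unspecified extension rule combined with a waiver of alpha adjustment would leave the primary claim open to challenge.

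**Working it through.** **Inputs.** From 9.1: yields of 25% (CCE) and 15% (CTC), margin 5 points, 10% attrition, looks at 40, 80, 120 and 160 per arm. From 9.2: success thresholds 98%, 98%, 98%, 96%. From 9.6: the 50% conditional-power limit. Assumed, because not stated: Beta(1,1) priors, and an extension to 240 or 320 per arm (480 or 640 in total).

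**1. The plan's own power figure.** For a single fixed analysis at one-sided 5% and 80% power:

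n = (1.645 + 0.842)² × (0.15×0.85 + 0.25×0.75) / (0.10 + 0.05)² = 6.18 × 0.315 / 0.0225 ≈ 87 per arm, or 97 after dividing by 0.9.

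For the planned four looks, exact binomial recursion gives power of 95.6% at 160 per arm and 93.7% at 144 per arm (160 × 0.9). The statement of more than 80% holds.

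**2. Type I error with 320 binding and no re-assessment.** This is evaluated at the boundary, CCE yield = CTC yield − 5 points. In the normal model the four statistics have correlation √(t_j/t_k) for j < k, with t = 0.25, 0.50, 0.75, 1 and critical values 2.054, 2.054, 2.054, 1.751. The chance of at least one crossing is 6.5%. The exact binomial result is 6.8% at a CTC yield of 15%, 6.7% at 20% and 6.6% at 25%. With only one interim, at 160 subjects, the same thresholds give 5.0% (exact 5.1-5.3%). The excess therefore comes from using three interims.

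**3. Adding the re-assessment.** At information fraction t with statistic Z, conditional power for the final analysis at 160 per arm is

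CP = Φ{[Z√t + θ(1 − t) − 1.751] / √(1 − t)}.

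Here θ = Z/√t under the observed trend. Under the design effect, θ = 0.15 × √160 / √0.315 = 3.38. Section 9.6 does not say which applies. The trial is extended when CP is at least 50%, with re-assessment at every interim. The binomial column covers CTC yields of 15-25%.

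| Reading of 9.6 | Binomial simulation | Normal model |
|---|---|---|
| No re-assessment | 6.6-6.8% | 6.5% |
| Observed trend, no looks past 320 | 6.5-6.7% | 6.4-6.5% |
| Observed trend, 98% looks continue | 6.9-7.3% | 6.8-7.1% |
| Design effect, no looks past 320 | 7.1-7.5% | 7.1-7.3% |
| Design effect, 98% looks continue | 7.6-8.6% | 7.6-8.4% |

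A separate simulation of the third row, with extension to 320 per arm and CTC yields of 12-25%, gave 7.1-7.4%. With a maximum of 480 per arm, the last row reaches 9.6% in the normal model.

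**4. Does the number of re-assessments matter?** Normal model, observed trend, extension to 320 per arm, 98% looks continuing: all three interims 7.1%, first interim only 7.0%, third interim only 6.5%. A single early re-assessment produces almost the whole rise. In the binomial simulation, re-assessment at the third interim only, with observed trend and no added looks, gives 6.1-6.4%, below the figure without re-assessment.

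**5. Thresholds that meet one-sided 5% with four looks.** In the normal model there are two examples:

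- Keep 98% at the interims and raise the final threshold to about 98.3%. Power is about 92%.
- Keep 96% at the final and raise the interims to about 99.1%. Power is about 95%.

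Both powers are for 160 per arm. At 144 per arm the drift is 3.38 × √0.9 = 3.21. The final look alone then gives at least Φ(3.21 − 2.11) ≈ 86% and Φ(3.21 − 1.75) ≈ 93%, so both options stay above 80% after attrition.

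**The case against.** The strongest reply is that 320 is the ceiling in every place a number is given, including the opening sentence of 9.6, and that no section states a larger one. On that reading, re-assessing the size means deciding whether the next block of 80 is needed, which fits the remark in 9.1 that the expected size is below 320. Re-assessment then adds no type I error. This stands in part: the text is an unreconciled and unspecified rule, not an explicit permission to exceed 320. It does not rescue the waiver of alpha adjustment, which has no purpose within the cap.

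A reader might infer that repeating the re-assessment at each interim is what inflates the error, or that a single re-assessment would be safe. The calculations do not support either inference. Re-assessing at all three interims under the observed trend with no added looks leaves the error unchanged, while one early re-assessment with continuing looks raises it. What matters is looks beyond 320, the effect assumed in conditional power, and timing.

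A reader might also attribute the whole excess over 5% to this rule. Most of it, about 1.5-1.8 points (6.5-6.8% less 5%), comes from four looks at the stated thresholds. The size of the rest depends on an assumed new maximum and on looks past 320, neither of which the documents state.

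**Conclusion.** The point holds as a failure to reconcile and specify. Either the rule in 9.6 has nothing to act on, or it permits an extension for which the waiver is not generally true.

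Under readings that the text does not exclude, one-sided type I error would be about 6.8-7.4% (continued 98% looks), 7.1-7.5% (design-effect conditional power) or 7.6-8.6% (both). Without re-assessment it is about 6.5-6.8%, and it does not rise above that with observed-trend conditional power and no looks past 320. The stated level is 5%.

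These figures rest on flat priors or a normal model, an extension to 240 or 320 per arm, and a one-sided 5%. With Beta(0.5,0.5) priors the figure without re-assessment is 6.8-7.5% at 160 per arm. If the 5% is two-sided (2.5% one-sided), the gap is wider.

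The change should be made, but it does not bear on the power claim, which is met comfortably.

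**What to change.** 1. Delete the sample-size adjustment and the no-alpha-adjustment sentence from 9.6. State that 320 is a binding cap and that conditional power serves futility only.
2. In 8.7, clarify that re-assessing the sample size means deciding whether to continue within the cap.
3. If an increase is wanted after all, state its maximum, the interim at which it may occur, the effect assumed in conditional power, and whether later looks continue and at what threshold.
4. In either case, state the prior and the sidedness of the 5% level, and show by simulation that type I error is at most 5%. A hard cap alone leaves about 6.5-6.8%. Raising the final threshold to about 98.3%, or the interim thresholds to about 99.1%, would serve. The alternative is to restate the error rate as about 6.5-7%.

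The wording change gives up only an option that the stated maximum already rules out. Recalibration lowers power from about 96% to about 92% or 95% at 160 per arm, still above the stated 80%.

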## 10.0 Risk/Benefit Analysis

CCE is well-tolerated by patients. As show in Table 1 in Section 6.2, no serious CCE-related AEs have been reported in 14 clinical studies (8-21). Most AEs are self-limiting, mild/moderate, effects of the bowel preparation regimen (nausea, vomiting, diarrhea, abdominal pain, headache, and vertigo). A full description of all reported AEs is included in the Risk Assessment Report, Post-Market Vigilance, and in the product Instructions for Use and Users Guide. This includes difficulty and/or inability to swallow the capsule, asymptomatic capsule retention, and nausea/vomiting. Patients also reported fatigue during the procedure due to the long prep and recording time.

## 11.0 Adverse Events and Complications

Adverse events will be collected at the start of the CCE/CTC bowel preparation and end with the OC Follow-up call (5-9 days after the unblinded OC procedure). During the course of the study the following AEs and serious adverse events (SAEs) will be collected:

- All adverse events related to the CCE, CTC and or OC procedures
- All retained capsules greater than 14 days
- All perforations
- All device deficiencies that may lead to a SAE
- All adverse events that meet serious adverse event definition in Section 11.2
- All deaths

### 11.1 Adverse Event

An AE is any untoward medical occurrence, unintended disease or injury, or untoward clinical signs (including abnormal laboratory findings) in subjects, users, or other persons, whether or not related to the investigational medical device. This definition includes events related to the investigational medical device or the comparator and the procedures involved. For users or other persons, this definition is restricted to events related to the investigational medical device.

AEs will be collected and documented until 5 – 9 days after the OC procedure, at which point the subject will be contacted by telephone, and will then be considered to have reached the end of the study.

NOTE: Documented pre-existing conditions are not considered to be reportable AEs unless there is a change in the nature or severity of the condition.

See Sections 11.10 and 11.11 for recording and reporting of AEs.

### 11.2 Serious Adverse Event

A serious adverse event (SAE) is one that:

- a) led to death,
- b) led to serious deterioration in the health of the subject that either resulted in

- 1) a life-threatening illness or injury, or
  - 2) a permanent impairment of a body structure or a body function, or
  - 3) in-patient or prolonged hospitalization, or
  - 4) medical or surgical intervention to prevent life threatening illness or injury or permanent impairment to a body structure or a body function, or
- c) Led to fetal distress, fetal death, or a congenital abnormality or birth defect.

NOTE: Planned hospitalization for a pre-existing condition or a procedure required by the clinical investigational plan, without serious deterioration in health, is not considered a SAE.

Some important medical events, although they may not result in death, be life-threatening, or require hospitalization may still be considered SAEs when, based upon appropriate medical judgment, they are felt to jeopardize the subject and may require medical or surgical intervention to prevent one of the outcomes listed above.

Life threatening means that the subject was, in the view of the investigator, at immediate risk of death from the reaction as it occurred. This does not include an AE that, if more severe, might have caused death.

Disability means a substantial disruption of a person's ability to conduct normal life's functions.

### **11.3 Adverse Device Effect (ADE)**

An Adverse Device Effect (ADE) is an occurrence related to or caused by the investigational device, procedure or comparator that is not serious. This includes use error or intentional abnormal use of the device. In addition inadequacies in the instructions for use, the deployment, the implantation, the installation, the operation, or any malfunction of the device are also included.

In the case of an ADE, OC should be postponed until the ADE is resolved and per physician discretion.

### **11.4 Serious Adverse Device Effect (SADE)**

A Serious Adverse Device Effect (SADE) is an adverse device effect, comparator, or procedure that has resulted in any of the consequences characteristic of a serious adverse event and is serious, but is not unanticipated.

### **11.5 Unanticipated Serious Adverse Device Effect (USADE)**

An Unanticipated Serious Adverse Device Effect (USADE) is a serious adverse device effect which by its nature, incidence, severity or outcome has not been identified in the current version of the risk analysis report.

### **11.6 Customer Complaint**

Any written, electronic, or verbal communication indicating a deficiency in the identity, quality, durability, reliability, safety, effectiveness, or performance of any product after it is released for distribution.

### 11.7 Adverse Event Severity Classification

Severity will be defined according to the following criteria:

Mild	Awareness of event, but easily tolerated
Moderate	Discomfort enough to cause some interference with activities of daily living (ADL)
Severe	Incapacitating, with an inability to perform ADL

An AE can be classified as severe and not deemed an SAE. Similarly, an SAE is not automatically severe in nature.

### 11.8 Adverse Event Relationship Classification

AE relationship to study procedures will be reported for 3 procedure types:

1. CCE (including capsule and/or sensors)
2. CTC Exam
3. Colonoscopy Exam

For each of the 3 procedure types above, relationship will be categorized as:

- *Not Related:* No relationship between the AE and the administration of any study procedure and a known relationship to other etiologies such as concomitant medications, non-study procedures, or the subject's clinical state.
- *Related:* An AE that follows a plausible temporal sequence from administration of a study procedure and follows a known response pattern to a study procedure. The reaction cannot be reasonably explained by the known characteristics of the subject's clinical state or other modes of therapy administered to the subject.
- *Impossible to Determine:* Given the information available, sequence and timing of events, it is impossible to determine the relationship of the AE with the study procedure.

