#### 9.4 Safety Analysis

Individual listings of AEs, including type of device, AEs (reported term) start date, duration, severity, and procedure-relatedness will be provided. Procedure relatedness will be assessed separately relative to the imaging modality and colonoscopy, as described in Section 11.8.

AEs will be summarized using frequency counts and percentages. Descriptive statistics will be provided by study arm and by severity and relationship, according to the definitions in Section 11.8. Comparisons between treatments of the proportions of subjects experiencing at least one AE, at least one SAE, at least one CCE/CTC device/procedure related AE, and at least one colonoscopy procedure related AE will be made using Chi-square test or Fisher's exact test as appropriate.

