### **17.3 Study Completion/Termination of Study**

Medtronic reserves the right to discontinue the study at any stage, with suitable written notice to all investigators, all reviewing IRB, and FDA.

Similarly, investigators may withdraw from the study at any time, subject to providing written notification to Medtronic 30 days prior to the date they intend to withdraw. However, Medtronic and investigators will be bound by their obligation to complete the follow-up of subjects already participating in the study. The subjects must be followed according to the clinical protocol, and information obtained during subject follow-up shall be reported to Medtronic on the appropriate eCRF.

Any USADE will be investigated immediately and, if the sponsor determines that unreasonable risk to subjects is possible, the study will be terminated and all regulating authorities and participating investigators will be notified.

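### The ADE, SADE and USADE definitions contradict one another, and the rule for Related shuts out events of a new kind, which leaves the only stated safety-specific termination trigger ambiguous

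*Combined protocol and SAP*

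**What the plan says.** All references are to the combined protocol and SAP.

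- **Section 11.3** defines an ADE as an occurrence "related to or caused by the investigational device, procedure or comparator that is not serious".
- **Section 11.4** defines a SADE as an adverse device effect with the consequences of a serious adverse event that "is serious, but is not unanticipated".
- **Section 11.5** defines the USADE class. Such an event, in its words, "is a serious adverse device effect which by its nature, incidence, severity or outcome has not been identified in the current version of the risk" (the yardstick is the risk analysis report).
- **Section 11.8** offers three relationship codes. Related applies to an event that has plausible timing "and follows a known response pattern to a study procedure", and that the subject's condition or other therapy cannot reasonably explain. Not Related needs the absence of a relationship "and a known relationship to other etiologies such as concomitant medications, non-study procedures, or the subject's clinical state". Impossible to Determine covers the rest.
- **Section 9.4** compares the arms on the proportion of subjects with "at least one CCE/CTC device/procedure related AE", among other measures. It does not say how Impossible to Determine is counted.
- **Section 17.3** gives the consequence: "Any USADE will be investigated immediately and, if the sponsor determines that unreasonable risk to subjects is possible, the study will be terminated". No other safety-specific termination criterion is stated; the early-stopping rule in Section 9.6 concerns futility.

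**The concern.** Two separate faults meet at the same place. The device-effect classes are built on one another, but each step adds a condition that the step before has ruled out. The relationship code also makes precedent a necessary condition for causation, so an event without precedent cannot be coded Related however strong the causal case.

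Both bear on serious events of a new kind, which are the events a safety trigger most needs to catch. The label matters because the reporting table in Section 11.11 gives serious adverse events, SADEs and USADEs the same 10-working-day deadline to the sponsor. Immediate investigation and the termination test come only with the USADE label. The medical monitor (Section 13.4) adjudicates only on request, so a mislabelled event is not certain to be corrected. The relationship code may also decide who counts in one of the between-arm tests in Section 9.4.

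**Working it through.** The plan gives no figure to reproduce on this point, so the check is mainly one of logic.

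**1. Can an event satisfy the class definitions?** Let R = related to or caused by the device, procedure or comparator; S = serious; U = unanticipated. Section 11.4 does not define U, so I take it to mean not identified in the risk analysis report, as in Section 11.5.

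| Class | Terms read as nested | Terms read as separate classes |
|---|---|---|
| ADE (11.3) | R and not S | R and not S |
| SADE (11.4) | ADE and S and not U = R and not S and S and not U: empty | R and S and not U |
| USADE (11.5) | SADE and U: empty, since SADE is empty and also excludes U | R and S and U |

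The nested reading follows the words, because Sections 11.4 and 11.5 each define their class through the class before it. It leaves two classes empty. The separate reading works, but the reader has to supply it.

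**2. How is an event of a new kind coded under Section 11.8?** Take an event with plausible timing, no known pattern and no other cause.

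- Related needs timing, a known pattern and no reasonable alternative explanation. It fails on the known pattern.
- Not Related needs a known other cause. It fails.
- Impossible to Determine is the only code left, even where the causal case is strong.

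**3. Does that code keep the event out of the USADE class?** Sections 11.3 to 11.5 and 17.3 do not cite the 11.8 codes, so the link is not stated. Section 11.8 is, however, the only place where the protocol says what related means, and Sections 8.5 and 9.4 both send the reader there. An investigator who applies it to Section 11.3 would leave the event out of the ADE class. One who reads Section 11.3 in its ordinary sense would not. The text does not settle which is intended.

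**4. Which events are affected?** The conditions in Section 11.5 are alternatives: nature, incidence, severity or outcome. A perforation, which Section 11.10 lists as a potential serious event, follows a known pattern. If its severity or outcome were not in the risk analysis report, it could be both Related and a USADE. Only an event new in nature meets the obstacle in step 2.

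**5. What is the scale in Section 9.4?** Let n be the subjects in an arm, r those with at least one Related event, and i those whose only candidate events are Impossible to Determine. The proportion is r/n under the strict code and (r + i)/n if those events count, a difference of i/n. The documents do not give i. At the planned maximum of 160 per arm, each such subject is worth 1/160 = 0.625 percentage points. If the study stops at the first look with 40 per arm, each is worth 1/40 = 2.5 points.

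**The case against.** The strongest reply is that this is loose drafting around a system that works. Much of that stands.

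- A reader might infer that the termination trigger can never be met. The documents do not support this. It would require the phrase in Section 11.5 to be the exact class defined in Section 11.4, whereas the reporting table in Section 11.11 names SADE and USADE separately and sets reporting duties for both.
- Nor does Section 11.8 by itself block a USADE. Its codes are not cited in the class definitions, and unidentified incidence, severity or outcome is enough under Section 11.5. Section 11.3 also includes use error and device malfunction without asking for any known pattern.
- Serious events reach the sponsor whatever their relationship code. Section 11.0 collects all serious adverse events, deaths and perforations; Section 11.11 sends serious events to the sponsor and has the sponsor's safety officer review all events for IRB reporting obligations. Section 17.3 also lets the sponsor discontinue at any stage.
- Section 9.4 compares the arms on any adverse event and any serious adverse event regardless of relationship, and it lists and summarises events by relationship. Indeterminate events therefore stay visible.
- A reader might also infer that the related-event comparison is biased low, and more so for CCE as the newer procedure. Section 9.4 does not say that indeterminate events are left out, not all of them need be truly related, and nothing in the documents shows that more would arise with CCE. Section 11.10 and Table 1 in fact describe known CCE events.

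The reply does not remove the conflict among Sections 11.3 to 11.5 or the mandatory known-pattern condition in Section 11.8. General reporting and a general right to stop are also not the same as the specific duty that Section 17.3 attaches to a USADE.

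**Conclusion.** The point holds in a limited form. The three class definitions contradict one another as written, and Section 11.8 sends a well-timed, otherwise unexplained event of a new kind to Impossible to Determine. The trigger in Section 17.3 is therefore ambiguous, particularly for such events, but not impossible to meet.

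The effect on Section 9.4 is conditional: these events leave the related-event comparison only if related there means the 11.8 code. Its size cannot be stated, because the documents give no expected number of indeterminate events. The per-subject scale above assumes the planned arm sizes as denominators. The primary endpoint is not affected. The change should be made because the text is wrong as it stands and is cheap to correct.

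**What to change.** - **Sections 11.3 to 11.5 and 17.3:** make the classes consistent. For example, drop the non-serious limit from 11.3. Then either drop the not-unanticipated clause from 11.4, so that USADE is a subset of SADE, or define SADE and USADE explicitly as the anticipated and unanticipated classes of serious ADE and reword 11.5 to match. Check that 17.3 refers to the class as redefined, and state whether ADE status rests on the 11.8 code.
- **Section 11.8:** stop making a known response pattern a mandatory condition for Related when timing is plausible and no alternative cause explains the event.
- **Section 9.4:** state what related means, and add a sensitivity analysis of the related-event comparison that counts Impossible to Determine as related. Counting all such events as related in the main comparison is debatable and is not needed here.

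The cost is an amendment to the wording, with the sponsor and IRB approval that Section 13.2 requires, and one extra analysis. No new data, visits or subjects are needed. Any events already coded Impossible to Determine would need a second look under the revised rule. The downside is that reported related-event rates may be slightly higher.
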